11.2 Antitumor Effect – Hematologic Tumors

Response in patients with lymphoma will be assessed using the International Working Group Consensus Response Evaluation Criteria In Lymphoma (RECIL 2017) (Younes et al., 2017).

11.2.1 CT/MRI measurements

Assessment of tumor burden will use the sum of the longest diameters (SLD). In subjects with disseminated disease, a maximum of 3 target lesions should be selected to estimate tumor response.

Target lesions should be selected per the following criteria:

- Target lesions should be selected from lesions of the largest size that can be measured reproducibly and preferably representing multiple sites and organs.
- Lymph nodes:
 - Lymph nodes can be considered target lesions if the lymph node longest diameter measures ≥ 15 mm.
 - A lymph node measuring between 10 and 14 mm is considered abnormal but should

not be selected as a target lesion.

- Lymph nodes measuring <10 mm in diameter are considered normal and cannot be used as target lesions.
 - In certain anatomical sites (inguinal, axillary, and portacaval), normal lymph nodes may exist in a narrow, elongated form, and such nodes should not be selected as target lesions if alternatives are available.
- Extranodal lesions are selected as target lesions if they have a soft tissue component, based on their size and the ease of reproducibility of repeated measurements, with a minimum measurement of the longest diameter of ≥ 15 mm.
- Nontarget lesions:
 - All other lesions should be identified as nontarget lesions and should be recorded at baseline, without the need to measure them.
 - Nontarget lesions should be followed and reported as present, absent, or clear progression.

11.2.2 FDG-PET measurements

FDG-PET is only required to confirm a CR.

Scoring is semi-quantitative using the Deauville 5-point scale (Deauville 5PS). It is a simple tool based on visual interpretation of [18F]2-fluoro-2-deoxy-D-glucose (FDG) uptake. It takes advantage of two reference points of the individual subject, which have demonstrated relatively constant uptake on serial imaging. The two reference organs are the mediastinum and the liver. The scale ranges from 1 to 5, where 1 is best and 5 is the worst. Each FDG-avid (or previously FDG-avid) lesion is rated independently:

1. no uptake or no residual uptake (when used interim)
2. slight uptake, but below blood pool (mediastinum)
3. uptake above mediastinal, but below or equal to uptake in the liver
4. uptake slightly to moderately higher than liver
5. markedly increased uptake or any new lesion (on response evaluation)

11.2.3 Bone marrow biopsy and aspirate

A bone marrow biopsy and aspirate are only required to confirm a CR.

11.2.4 RECIL 2017: Response categories based on assessment of target lesions

	% Change in sum of diameters of target lesions from nadir				
	CR	PR	MR ^a	SD	PD
% change from baseline	
● Complete disappearance of all target lesions and all nodes with long axis <10 mm● $\geq 30\%$	$\geq 30\%$ decrease in the sum of longest diameters of target lesions but not a CR	$\geq 10\%$ decrease in the sum of longest diameters of target lesions but not a PR ($<30\%$)	<10% decrease or $\leq 20\%$ increase in the sum of longest diameters of target lesions	
● $>20\%$ increase in the sum of longest diameters of target lesions● For small lymph nodes

	% Change in sum of diameters of target lesions from nadir				
	CR	PR	MR ^a	SD	PD
	decrease in the sum of longest diameters of target lesions (PR) with normalization of FDG-PET				measuring <15 mm post therapy, a minimum absolute increase of 5 mm and the long diameter should exceed 15 mm • Appearance of a new lesion
FDG-PET	Normalization of FDG-PET (Deauville score 1-3)	Positive (Deauville score 4-5)	Any	Any	Any
Bone marrow involvement	Not involved	Any	Any	Any	Any
New lesions	No	No	No	No	Yes or No

CR, complete response; CT, computerized tomography; FDG-PED, [¹⁸F]2-fluoro-2-deoxy-D-glucose; MR, minor response; PD, progression of disease; PR, partial response; SD, stable disease

^a A provisional category. Table is as shown in (Younes et al., 2017).

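### The lymphoma response table names both nadir and baseline as reference for the same size thresholds, so from the second post-baseline scan one set of measurements can be PR/CR under one label and MR, SD or PD under the other

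*Combined protocol and SAP*

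**What the plan says.** Section 11.2 assigns lymphoma response to RECIL 2017, and Section 11.2.4 gives the table of categories, with a footnote saying that it follows the cited publication.

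- **Header.** Above CR, PR, MR, SD and PD the table reads "Change in sum of diameters of target lesions from nadir". The header is printed again where the table continues.
- **Row label.** The row that carries the size thresholds is labelled percent "change from baseline".
- **Cells.** PR is a 30% or greater "decrease in the sum of longest diameters of target lesions but not a CR". MR is a 10% or greater "decrease in the sum of longest diameters of target lesions but not a PR", that is, under 30%. PD is a more than 20% "increase in the sum of longest diameters of target lesions". No cell names its own reference.
- **Rest of 11.2.** Sections 11.2.1 to 11.2.3 cover lesion selection, PET and marrow, and give no reference rule.
- **Solid tumors.** Section 11.1.4 does set the reference by category: PR against the baseline sum, PD against the smallest sum on study. It applies to solid tumors only.
- **PET.** Section 11.2.2 says "FDG-PET is only required to confirm a CR". In the table's PET row the CR cell reads "Normalization of FDG-PET (Deauville score 1-3" and the PR cell reads "Positive (Deauville score 4-5", while MR, SD and PD accept any result.

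**The concern.** A decrease and an increase need different references. Shrinkage accumulates over several scans, so a response is naturally judged against where the patient started. Progression is regrowth, so it is naturally judged against the best point reached. A table with one reference in its header and another in its row label leaves the assessor to choose, and neither label works if it is applied to every column. Measured from nadir, a gradual responder may never reach the PR threshold. Measured from baseline, regrowth after a good response may not count as PD until the sum is well above its starting value.

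Antitumor activity is a secondary objective (Section 1.2). The category also matters for the individual patient. Section 5.5 lists progression among the reasons treatment ends, and Section 5.2 makes stable or progressed disease a condition for intra-patient escalation. Section 8.2 plans at least 5 lymphoma patients. The response list in Section 8.3.1 has no MR category, so a PR reread as MR has no named place in the analysis.

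**Working it through.** The plan gives no figure to reproduce here. The check applies the table's thresholds to assumed sums of diameters under each reference.

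**Inputs from 11.2.4.** PD: increase above 20%. Response range: decrease of 30% or more (CR if PET is normal, PR if PET is positive). MR: decrease of 10% to under 30%. SD: otherwise.

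**Assumptions.** Baseline sum 100; no new lesion; marrow not involved; target lesions still present. The separate absolute-size rule for small nodes is not modelled.

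**Formulas.** Change from baseline = current/baseline - 1. Change from nadir = current/(smallest earlier sum) - 1.

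**Gradual shrinkage, sums 100, 80, 64, 56**

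| Scan | From baseline | Category | From nadir | Category |
|---|---|---|---|---|
| 80 | 80/100 - 1 = -20% | MR | 80/100 - 1 = -20% | MR |
| 64 | 64/100 - 1 = -36% | PR/CR | 64/80 - 1 = -20% | MR |
| 56 | 56/100 - 1 = -44% | PR/CR | 56/64 - 1 = -12.5% | MR |

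Under the header's reference this patient never responds.

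**Regrowth, sums 100, 50, 62**

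| Scan | From baseline | Category | From nadir | Category |
|---|---|---|---|---|
| 50 | -50% | PR/CR | -50% | PR/CR |
| 62 | 62/100 - 1 = -38% | PR/CR | 62/50 - 1 = +24% | PD |

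Under the row label's reference, PD by size would need a sum above 120. From a nadir of 50 that is a rise of more than 120/50 - 1 = 140%.

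**Other pairs (baseline 100)**

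- Nadir 60, now 62: -38% against +3.3%, so PR/CR against SD.
- Nadir 70, now 86: -14% against +22.9%, so MR against PD.

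**Range of disagreement.** The two references were compared over prior nadirs of 5 to 100 and current sums of 5 to 150. With a PET result in hand, no set of measurements received more than two categories, and PR and CR were never both possible. At the first post-baseline scan the nadir is the baseline, so the references agree.

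**Effect on the response rate.** Section 8.3.1 defines one main response-rate analysis over all eligible patients. Section 8.2 gives 21 to 33 evaluable patients and a ceiling of 40. One patient is therefore 1/40 = 2.5, 1/33 = 3.0 or 1/21 = 4.8 percentage points.

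**The case against.** **Convention and source.** An experienced assessor will probably infer the usual split, with response from baseline and progression from nadir. The footnote also defers to a cited publication that may resolve the labels. That lowers the practical risk, but the protocol states no such split for lymphoma, and the publication cannot be checked from these documents. The table is also broken across pages in the text available, so the exact span of the header is not certain. It does stand above all five category names each time it appears.

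**The row label should prevail.** Scoring a gradual responder from nadir is strained when the threshold row itself says baseline. That is fair. But the same row holds the PD threshold, and following its label there misses the regrowth case.

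**No response is lost on regrowth.** This stands. In 100, 50, 62 the patient is already a responder at 50 under both readings. Only the progression call and the duration of response change.

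**Stronger readings that the documents do not support**

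- A reader might infer that one set of scans could be scored PR, MR, CR or PD at will. Once PET is known, at most two categories are possible.
- A reader might infer that the PET wording is a flat contradiction that makes CR and PR interchangeable. The CR cell itself labels a decrease of 30% or more as PR, raised to CR by a normal PET, and the PR cell excludes only a CR. With 11.2.2, the natural reading is that such a decrease without PET is PR. Nor does the PET result move the combined CR and PR rate. What remains is that the PR cell of the PET row has no entry for PET not done.
- A reader might divide by the 5 lymphoma patients and claim 20 points of response rate. Five is a minimum, and no lymphoma-only rate is defined.
- A reader might infer that the RP2D is at risk. Section 2.3 lists patient responses among its determinants, but the operative rules in Sections 5.2 and 8.1 rest on first-cycle DLTs.

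**Conclusion.** The table is wrong as written on the reference point. From the second post-baseline scan, identical lymphoma measurements can be a response under one label and MR, SD or PD under the other, and no text in 11.2 decides between them. The reach is limited to a secondary endpoint without a formal test and to the progression call in at least 5 patients. A gradual responder scored the wrong way changes the all-patient response rate by about 2.5 to 4.8 points; a regrowth case changes the progression call, not the response. The effect of a PD call is itself not uniform, because Section 5.2 allows escalation for some patients whose disease has progressed.

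The sums used are illustrative. They show that the categories can differ, not how often they will. The conclusion also assumes that no rule outside these documents is already being applied. The PET entry is a minor clarification only.

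**What to change.** Replace the single header and row label in 11.2.4 with a reference for each category, using for PR and PD the references that 11.1.4 already gives for solid tumors:

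- CR, PR and MR: decrease measured against the baseline sum.
- PD: increase measured against the smallest sum on study, baseline included.
- SD: neither a response (including MR) nor a PD threshold is met.
- Precedence: PD when both a response threshold and the PD threshold are met.

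The precedence line is needed because 100, 50, 62 meets both thresholds once the references differ. Under these rules 100, 80, 64, 56 becomes a response from the scan at 64, and 100, 50, 62 is PD at the scan at 62.

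In the PET row, add *or not done* to the PR cell, so that a decrease of 30% or more without PET is scored PR, in line with 11.2.2.

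The cost is a wording change to one table, to be compared with the cited publication when it is made. No additional PET, scan or patient is required.

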12. STUDY OVERSIGHT AND DATA REPORTING / REGULATORY REQUIREMENTS

Adverse event lists, guidelines, and instructions for AE reporting can be found in [Section 9](#).

12.1 Study Oversight

This protocol is monitored at several levels, as described in this section. The Protocol Principal Investigator is responsible for monitoring the conduct and progress of the clinical trial, including the ongoing review of accrual, patient-specific clinical and laboratory data, and routine and serious adverse events; reporting of expedited adverse events; and accumulation of reported adverse events from other trials testing the same drug(s). The Protocol Principal Investigator and statistician have access to the data at all times through the CTMS web-based reporting portal.

For the Phase 1 portion of this study, all decisions regarding dose escalation/expansion/de-escalation require sign-off by the Protocol Principal Investigator through the CTMS/IWRS. In addition, for the Phase 1 portion, the Protocol Principal Investigator will have at least monthly, or more frequently, conference calls with the Study Investigators and the CTEP Medical Officer(s) to review accrual, progress, and adverse events and unanticipated problems.

All Study Investigators at participating sites who register/enroll patients on a given protocol are responsible for timely submission of data via Medidata Rave and timely reporting of adverse events for that particular study. This includes timely review of data collected on the electronic CRFs submitted via Medidata Rave.

All studies are also reviewed in accordance with the enrolling institution's data safety monitoring plan.

12.2 Data Reporting

Medidata Rave is a clinical data management system being used for data collection for this trial/study. Access to the trial in Rave is controlled through the CTEP-IAM system and role assignments.

Requirements to access Rave via iMedidata:

- A valid account, and
- Assigned a Rave role on the LPO or PO roster at the enrolling site of: Rave CRA, Rave Read Only, Rave CRA (Lab Admin), Rave SLA, or Rave Investigator.

Rave role requirements:

- Rave CRA or Rave CRA (Lab Admin) role, must have a minimum of an Associate Plus (AP) registration type,
- Rave Investigator role, must be registered as an Non-Physician Investigator (NPIVR) or Investigator (IVR), and
- Rave Read Only role, site staff must have at a minimum an Associates (A) registration type.

- Refer to <https://ctep.cancer.gov/investigatorResources/default.htm> for registration types and documentation required.

If the study has a DTL, individuals requiring write access to Rave must also be assigned the appropriate Rave tasks on the DTL.

Upon initial site registration approval for the study in Regulatory Support System (RSS), all persons with Rave roles assigned on the appropriate roster will be sent a study invitation e-mail from iMedidata. To accept the invitation, site staff must log in to the Select Login (<https://login.imedidata.com/selectlogin>) using their CTEP-IAM username and password, and click on the *accept* link in the upper right-corner of the iMedidata page. Site staff will not be able to access the study in Rave until all required Medidata and study specific trainings are completed. Trainings will be in the form of electronic learnings (eLearnings), and can be accessed by clicking on the link in the upper right pane of the iMedidata screen. If an eLearning is required and has not yet been taken, the link to the eLearning will appear under the study name in iMedidata instead of the *Rave EDC* link; once the successful completion of the eLearning has been recorded, access to the study in Rave will be granted, and a *Rave EDC* link will display under the study name.

Site staff that have not previously activated their iMedidata/Rave account at the time of initial site

registration approval for the study in RSS will receive a separate invitation from iMedidata to activate their account. Account activation instructions are located on the CTSU website in the Data Management section under the Rave resource materials (Medidata Account Activation and Study Invitation Acceptance). Additional information on iMedidata/Rave is available on the CTSU members' website in the Data Management > Rave section at www.ctsu.org/RAVE/ or by contacting the CTSU Help Desk at [name] or by e-mail at [contact].

12.2.1 Method

This study will be monitored by the Clinical Trials Monitoring Service (CTMS). Data will be submitted to CTMS at least once every two weeks via Medidata Rave (or other modality if approved by CTEP). Information on CTMS reporting is available at <http://www.theradex.com/clinicalTechnologies/?National-Cancer-Institute-NCI-11>. On-site audits will be conducted three times annually (one annual site visit and two data audits). For CTMS monitored studies, after users have activated their accounts, please contact the Theradex Help Desk at [contact] or by email at [contact] for additional support with Rave and completion of CRFs.

12.2.2 Responsibility for Data Submission

For ETCTN trials, it is the responsibility of the PI(s) at the site to ensure that all investigators at the ETCTN Sites understand the procedures for data submission for each ETCTN protocol and that protocol specified data are submitted accurately and in a timely manner to the CTMS via the electronic data capture system, Medidata Rave.

Data are to be submitted via Medidata Rave to CTMS on a real-time basis, but no less than once every 2 weeks. The timeliness of data submissions and timeliness in resolving data queries will be tracked by CTMS. Metrics for timeliness will be followed and assessed on a quarterly basis. For the purpose of Institutional Performance Monitoring, data will be considered delinquent if it is greater than 4 weeks past due.

Data from Medidata Rave and CTEP-AERS is reviewed by the CTMS on an ongoing basis as data is received. Queries will be issued by CTMS directly within Rave. The queries will appear on the Task Summary Tab within Rave for the CRA at the ETCTN to resolve. Monthly web-based reports are posted for review by the Drug Monitors in the IDB, CTEP. Onsite audits will be conducted by the CTMS to ensure compliance with regulatory requirements, GCP, and NCI policies and procedures with the overarching goal of ensuring the integrity of data generated from NCI-sponsored clinical trials, as described in the ETCTN Program Guidelines, which may be found on CTEP (http://ctep.cancer.gov/protocolDevelopment/electronic_applications/adverse_events.htm) and CTSU websites.

An End of Study CRF is to be completed by the PI and is to include a summary of study endpoints not otherwise captured in the database, such as (for phase 1 trials) the recommended phase 2 dose (RP2D) and a description of any dose-limiting toxicities (DLTs). CTMS will utilize a core set of eCRFs that are Cancer Data Standards Registry and Repository (caDSR) compliant (<http://cbiit.nci.nih.gov/ncip/biomedical-informatics-resources/interoperability-and->

semantics/metadata-and-models). Customized eCRFs will be included when appropriate to meet unique study requirements. The PI is encouraged to review the eCRFs, working closely with CTMS to ensure prospectively that all required items are appropriately captured in the eCRFs prior to study activation. CTMS will prepare the eCRFs with built-in edit checks to the extent possible to promote data integrity.

CDUS data submissions for ETCTN trials activated after March 1, 2014, will be carried out by the CTMS contractor, Theradex. CDUS submissions are performed by Theradex on a monthly basis. The trial's lead institution is responsible for timely submission to CTMS via Rave, as above.

Further information on data submission procedures can be found in the ETCTN Program Guidelines (http://ctep.cancer.gov/protocolDevelopment/electronic_applications/adverse_events.htm).

12.3 Data Quality Portal

The Data Quality Portal (DQP) provides a central location for site staff to manage unanswered queries and form delinquencies, monitor data quality and timeliness, generate reports, and review metrics.

The DQP is located on the CTSU members' website under Data Management. The Rave Home section displays a table providing summary counts of Total Delinquencies and Total Queries. DQP Queries, DQP Delinquent Forms, and the DQP Reports modules are available to access details and reports of unanswered queries, delinquent forms, and timeliness reports. Review the DQP modules on a regular basis to manage specified queries and delinquent forms.

The DQP is accessible by site staff that are rostered to a site and have access to the CTSU website. Staff that have Rave study access can access the Rave study data using a direct link on the DQP.

To learn more about DQP use and access, click on the Help icon displayed on the Rave Home, DQP Queries, and DQP Delinquent Forms modules.

Note: Some Rave protocols may not have delinquent form details or reports specified on the DQP. A protocol must have the Calendar functionality implemented in Rave by the Lead Protocol Organization (LPO) for delinquent form details and reports to be available on the DQP. Site staff should contact the LPO Data Manager for their protocol regarding questions about Rave Calendaring functionality.

12.4 Collaborative Agreements Language

The agent supplied by CTEP, DCTD, NCI used in this protocol is provided to the NCI under a Collaborative Agreement (CRADA) between the Pharmaceutical Company (hereinafter referred to as "Collaborator") and the NCI Division of Cancer Treatment and Diagnosis. Therefore, the following obligations/guidelines, in addition to the provisions in the "Intellectual Property Option

to Collaborator”

(http://ctep.cancer.gov/industryCollaborations2/intellectual_property.htm) contained within the terms of award, apply to the use of the Agent(s) in this study:

1. Agent may not be used for any purpose outside the scope of this protocol, nor can Agent be transferred or licensed to any party not participating in the clinical study. Collaborator data for Agent are confidential and proprietary to Collaborator and shall be maintained as such by the investigators. The protocol documents for studies utilizing Agents contain confidential information and should not be shared or distributed without the permission of the NCI. If a copy of this protocol is requested by a patient or patient's family member participating on the study, the individual should sign a confidentiality agreement. A suitable model agreement can be downloaded from: <http://ctep.cancer.gov>.
2. For a clinical protocol where there is an investigational Agent used in combination with another Agent, each the subject of different Collaborative Agreements, the access to and use of data by each Collaborator shall be as follows (data pertaining to such combination use shall hereinafter be referred to as "Multi-Party Data"):
 - a. NCI will provide all Collaborators with prior written notice regarding the existence and nature of any agreements governing their collaboration with NCI, the design of the proposed combination protocol, and the existence of any obligations that would tend to restrict NCI's participation in the proposed combination protocol.
 - b. Each Collaborator shall agree to permit use of the Multi-Party Data from the clinical trial by any other Collaborator solely to the extent necessary to allow said other Collaborator to develop, obtain regulatory approval or commercialize its own Agent.
 - c. Any Collaborator having the right to use the Multi-Party Data from these trials must agree in writing prior to the commencement of the trials that it will use the Multi-Party Data solely for development, regulatory approval, and commercialization of its own Agent.
3. Clinical Trial Data and Results and Raw Data developed under a Collaborative Agreement will be made available to Collaborator, the NCI, and the FDA, as appropriate and unless additional disclosure is required by law or court order as described in the IP Option to Collaborator (http://ctep.cancer.gov/industryCollaborations2/intellectual_property.htm). Additionally, all Clinical Data and Results and Raw Data will be collected, used and disclosed consistent with all applicable federal statutes and regulations for the protection of human subjects, including, if applicable, the *Standards for Privacy of Individually Identifiable Health Information* set forth in 45 C.F.R. Part 164.
4. When a Collaborator wishes to initiate a data request, the request should first be sent to the NCI, who will then notify the appropriate investigators (Group Chair for Cooperative Group studies, or PI for other studies) of Collaborator's wish to contact them.
5. Any data provided to Collaborator for Phase 3 studies must be in accordance with the guidelines and policies of the responsible Data Monitoring Committee (DMC), if there is a

DMC for this clinical trial.

6. Any manuscripts reporting the results of this clinical trial must be provided to CTEP by the Group office for Cooperative Group studies or by the principal investigator for non-Cooperative Group studies for immediate delivery to Collaborator for advisory review and comment prior to submission for publication. Collaborator will have 30 days from the date of receipt for review. Collaborator shall have the right to request that publication be delayed for up to an additional 30 days to ensure that Collaborator's confidential and proprietary data, in addition to Collaborator's intellectual property rights, are protected. Copies of abstracts must be provided to CTEP for forwarding to Collaborator(s) for courtesy review as soon as possible and preferably at least three (3) days prior to submission, but in any case, prior to presentation at the meeting or publication in the proceedings. Press releases and other media presentations must also be forwarded to CTEP prior to release. Copies of any manuscript, abstract and/or press release/ media presentation should be sent to:
[contact]

The Regulatory Affairs Branch will then distribute them to Collaborator. No publication, manuscript or other form of public disclosure shall contain any of Collaborator's confidential/proprietary information.

